7.1 Specification of Safety Parameters

Our study protocol is designed to minimize AEs with this population. Because electrical stimulation is prohibited, the needling treatment will be safe for patients with pacemakers. This study will comply with the national standard requiring acupuncturist to use only single-use (one-time use), pre-sterilized needles that are discarded immediately after use. This practice reduces

risk of transfer of blood-borne pathogens and is already required of all acupuncture providers in all states where this pragmatic trial will be implemented. Acupuncturists are trained to avoid areas of the body where there are rashes, skin lesions or any breach in normal skin barrier. They will have flexibility in positioning the patient for treatment so that it is comfortable for the patient. Finally, patients whose symptoms significantly worsen will be referred to their PCP within their healthcare system.

7.2 Methods and Timing for Assessing, Recording, and Analyzing Safety Parameters

Acupuncture has an excellent safety profile. Collectively, several large studies gathering data on adverse events from more than 235,000 patients^{33,34} and involving more than 63,000 treatments provided by 156 clinicians^{35,36} found that minor adverse events, for example bleeding or needle pain, are the most common, in the range of 1–10 in 100 patients for bleeding and hematoma and only 1–10 in 1000 for strong pain during needling.³⁴ Further, Hopton³⁷ found no evidence that patients who reported bothersome treatment reactions were less willing to try acupuncture again than those who did not, suggesting that most patients perceive common adverse events as minor. In a large trial of acupuncture for cLBP, 2.3% of patients reported a moderate adverse experience that was deemed likely due to treatment and only 1 of 477 reported pain lasting one month.²⁵ The most commonly reported AEs were short-term pain, with one participant reporting dizziness and another, back spasms. Because acupuncture involves needle insertion, transient pain is possible, especially at acupoints in more sensitive regions of the body. The most serious adverse events, such as pneumothorax, infection, organ or tissue injury, persistent nerve pain, or needle breakage are very rare (typically 1 in 100,000 or less).³⁴

AEs reported by patients to their acupuncturists or study staff will be recorded and reported to appropriate regulatory bodies (single IRB and Independent Monitoring Committee (IMC)). Acupuncturists will record AEs on their treatment forms but alert the research team immediately if they are concerned about any AE or learn a participant is injured, needs hospitalization, trip to the emergency department or medical attention. In addition, patients will have the phone numbers of study staff to report any side effects they are concerned about in real time. We will collect data on “health problems that have interfered with your functioning for a few days or more that you think may have been caused by your study acupuncture treatment” using a mailed questionnaire sent to all acupuncture-randomized participants at 3 months after randomization and enhanced acupuncture participants again at 6 months after randomization. Any positive responses will be reviewed by study medical personnel and followed up by study personnel to obtain additional information on the patient’s condition, whether it has resolved or not, how long that took and whether the patient needed to modify their activities. The previous AE form we used for an acupuncture study (which we filled out based on data from the follow-up interview) included: anxiety, bruising, dizziness, fainting, fatigue, headache, nausea/vomiting, pain from needle insertion or stimulation, and other pain (including increased back pain). We graded non-serious AEs as mild, moderate and severe. We also included information on relatedness to treatment (definitely, probably, possibly, definitely not). Note, increased back pain is an expected variation in the natural history of cLBP and, as such, would not without concomitant disability be considered an AE for this study.

7.3 Adverse Events and Serious Adverse Events

Acupuncture can have transient side effects as described in the previous section. For the proposed study, we are operationally defining a serious adverse event (SAE) as a death, hospitalization, prolongation of a hospitalization, or other serious or life-threatening event during a patient’s active participation in the trial. We will review/query active study participants’ EHR

data every month to identify deaths and hospitalizations among enrolled participants. In the case of a death, a chart review will be conducted by a physician at the clinical site to assess whether the death was related to the study intervention (definitely, probably, possibly, or unrelated to the study intervention). For hospitalizations, a study clinician at each HCS will review the list of diagnoses for possible relatedness to the acupuncture intervention. For any diagnosis at least possibly related to acupuncture, a more in-depth examination of the medical chart will be conducted. Because the number of hospitalizations in our older adult study population may be high and acupuncture poses only minimal risk, we do not plan to chart-review hospitalizations as a matter of course. However, if our analytic reports suggest a possible increased risk of hospitalizations associated with acupuncture, we will work with our monitoring groups to develop a plan to do chart reviews on all or a subset of patients charts who were hospitalized. A non-serious AE will be defined as an unfavorable and unintended diagnosis, symptom, syndrome, or disease that occurs or worsens during the acupuncture intervention period and is plausibly related to acupuncture. We believe this definition is appropriate, given that older adults have many diagnoses, symptoms, and syndromes, most of which would be expected to be of longer duration and unrelated to acupuncture, for which AEs have typically been shown to be relatively brief in duration. Non-serious AEs will be collected in multiple ways: (1) at 3 and 6 months using a mailed questionnaire sent to all acupuncture-randomized participants at 3 months after randomization and enhanced acupuncture participants again at 6 months after randomization asking about “health problems that have interfered with your functioning for a few days or more that you think may have been caused by your study acupuncture treatment” ; (2) from participants who may phone the study team at any time to report AEs; and (3) via electronic acupuncturist treatment reports for events that occur or were reported in the acupuncturist’s office. Because acupuncture has relatively short-term physiological effects, we will not report AEs that first manifest more than 30 days after a participant’s final acupuncture treatment.

We will classify each non-Serious AE using the following definitions: Mild (transient or minimal symptoms; no changes in activity level; no therapy or only symptomatic therapy); Moderate (symptomatic with moderate changes in activity level; no decrease in social activities; specific therapy required); Severe (incapacitating; bed rest; substantial decrease in social activities; loss of work). These definitions are consistent with the International Council for Harmonisation (ICH) standards in characterizing AEs. In the unlikely event that an adverse effect occurs that requires medical care, treatment will be provided according to each participants’ existing health care coverage. We will also assess the likely relatedness of the adverse event and acupuncture given the nature of the event, the timing related to treatment and any important contextual factors.

Unanticipated problems that include risks to participants or others are defined by the Office for Human Research Protections as any incident, experience or outcomes that meets all the following criteria:

1. Unexpected in terms of nature, severity, or frequency given (a) the research procedures that are described in the protocol-related documents, such as the IRB-approved research protocol and informed consent document; and (b) the characteristics of the subject population being studied;
2. Related or possibly related to participation in the research (“possibly related” means there is a reasonable possibility that the incident, experience, or outcome may have been caused by the procedures involved in the research); and

3. Suggests that the research places subjects or others at a greater risk of harm (including physical, psychological, economic, or social harm) than was previously known or recognized.

Unanticipated problems will be recorded in the data collection system throughout the trial.

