4. SELECTION AND ENROLLMENT OF PARTICIPANTS

We plan to recruit a total of 789 participants with chronic low back pain that has persisted for at least three months. Participants will be recruited from four health care systems: IFH (n =123); KPNC (n=288); KPWA (n=174) and SH (n=204). The number of participants recruited from each site may increase by up to 25% from these targets at IFH, KPNC, and SH and may increase by up to 50% from the recruitment target at KPWA with the total number not to exceed 820 participants.

For Aim 3, we plan to recruit and interview 10 participants from each of the four health care systems (n=40) that have been randomized to an acupuncture arm (SA or EA) to learn about their study and acupuncture experiences. We also plan to recruit, survey, and/or interview up to 60 study acupuncturists across the four health care systems to learn about their experience delivering acupuncture as part of the study and more broadly in their community. We will recruit national stakeholders including policy experts, acupuncturists, clinicians that provide acupuncture, and acupuncture researchers that have a vested interest in acupuncture policy around treating older adults to learn more about the impact of the CMS policy for reimbursement for acupuncture treatment on the national landscape for acupuncture reimbursement. We will recruit up to 50 and interview up to 25 stakeholders.

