Acupuncture implementation costs will be captured from study records in terms of the number of treatments received in 15-minute units and valued at typical community rates. For the payer perspective, we will use several assumptions regarding the amount of these costs reimbursed by Medicare with our base case based on typical acupuncture reimbursement rates (or trial allowable costs per Medicare). We would prefer to capture all healthcare utilization and cost data for the year before and after baseline from CMS for each patient in the study. However, this is unlikely given the time constraints of our project and when Medicare data are available. In addition, Medicare/CMS data will not include healthcare utilization for those not currently on Medicare (e.g., still on employer insurance or getting care at the VA). Since KPNC and KPWA tend to provide all care for their patients, we should be able to capture full healthcare utilization from their EHRs and price it using Medicare rates. SH provides most of their participants' care and we will explore whether we can use a similar pricing scheme for their participants. However, IFH only provides primary care. Therefore, the IFH EHR will only contain information on primary care-related healthcare utilization and incomplete information on referrals to specialists and hospitalizations. We will be limited to the data we can obtain in a timely manner from Medicare for IFH participants.

A bootstrap methodology will be used to estimate confidence intervals,^{111,112} and one-way sensitivity analyses will be performed to determine the robustness of our estimates with different assumptions such as the reimbursement rate for acupuncture and the inclusion of back-pain related costs only.¹⁰⁶

The cost-effectiveness analysis will be conducted by [name] with assistance from [name] at RAND in Santa Monica, California using de-identified data obtained from the Coordinating Center.

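### Hospitalizations, part of the SAE definition, are found by monthly EHR query at every site, yet the protocol says the IFH EHR is incomplete for hospitalizations, so SAEs at IFH are likely under-counted

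*Protocol*

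**What the plan says.** Protocol 7.3 defines a "serious adverse event (SAE) as a death, hospitalization, prolongation of a hospitalization, or other serious or life-threatening event" during active participation. It finds deaths and hospitalizations by querying EHR "data every month to identify deaths and hospitalizations among enrolled participants"; SAP 19.2 uses the same method. A study clinician at each health care system then reviews the diagnoses for possible relatedness. Hospital charts are not reviewed routinely. A wider chart-review plan is considered only "if our analytic reports suggest a possible increased risk of hospitalizations associated with acupuncture". SAP 5.3 puts all randomized participants in the safety sample for 12 months, and SAP 19.5 summarizes safety outcomes by arm without a formal SAE test.

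Protocol 9.6, writing about costs, describes the IFH record differently: "the IFH EHR will only contain information on primary care-related healthcare utilization and incomplete information on referrals to specialists and hospitalizations". It adds: "We will be limited to the data we can obtain in a timely manner from Medicare for IFH participants". SAP 18 also says that IFH provides only primary care and is outside the data warehouse used to capture utilization at the other sites, and that the team will explore comparable IFH data.

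The other safety routes are these:

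- **Acupuncturists** (Protocol 7.2) record adverse events on treatment forms and must "alert the research team immediately if they are concerned about any AE or learn a participant is injured, needs hospitalization".
- **AE questionnaire** (Protocol 7.2 and 7.3): it goes to SA and EA participants at 3 months and to EA again at 6 months. It asks about problems attributed to study acupuncture. The SAP 19.1 question, at 3, 6 and 12 months, is also about the acupuncture treatments.
- **Phone line** (Protocol 7.2 and 7.3): participants may call the study staff about side effects or adverse events.

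**The concern.** The same EHR is called incomplete for hospitalizations in the cost section and used without comment to find hospitalizations in the safety section. The investigators saw the gap and planned around it for costs, but neither workaround is linked to SAE capture. No other safety route asks every participant about hospital stays.

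Two things are at stake. First, an IFH hospitalization that never enters the EHR also misses the clinician's diagnosis review and, through it, the six-monthly SAE report to the Independent Monitoring Committee. Second, the by-arm hospitalization count decides whether wider chart review is considered. With no formal test planned, those counts will be read as they stand, so their completeness matters.

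**Working it through.** **Share of the trial affected.** SAP 4 puts IFH at 16% of the expected sample. The site targets in Protocol 4 are 123, 288, 174 and 204, which sum to 789. 123/789 = 15.6%, so the plan's figure is reproduced. At 1:1:1 this is 41 per arm: 41 UMC and 82 acupuncture. Protocol 4 lets IFH grow by up to 25% within a cap of 820; 123 × 1.25 / 820 = 18.8% is the upper limit.

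**Events missed at IFH.** The documents give neither a hospitalization rate nor a capture rate, so these are assumptions:

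- h, proportion hospitalized in 12 months (one event per person, equal in all arms): 0.10 to 0.20
- q, proportion of IFH hospitalizations visible in the IFH EHR: 0.30 to 0.70

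Missed = 123 × h × (1 − q)

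- Low: 123 × 0.10 × 0.30 = 3.7
- High: 123 × 0.20 × 0.70 = 17.2

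That is about 4 to 17 events, or 1.2 to 5.7 per arm. If the other sites are complete, the trial-wide count is too low by 0.156 × (1 − q), or 4.7% to 10.9%.

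**Arm difference, only if acupuncturist alerts are added to the by-arm count.** A further assumption is that acupuncturists recover 30-60% of the missed events that occur during treatment contact. Contact lasts 3 of 12 months in SA and 6 of 12 in EA. With events spread evenly over the year, average contact is (0.25 + 0.50)/2 = 0.375. Effective recovery e is 0.30 × 0.375 = 0.1125 to 0.60 × 0.375 = 0.225. UMC recovery by this route is zero.

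IFH ratio, acupuncture:UMC, when the true ratio is 1: [q + (1 − q)e]/q

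- Low (q = 0.70, e = 0.1125): 1 + (0.30/0.70) × 0.1125 = 1.05
- High (q = 0.30, e = 0.225): 1 + (0.70/0.30) × 0.225 = 1.53

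Trial-wide ratio, with complete capture in the other (789 − 123)/3 = 222 participants per arm: 1 + 41(1 − q)e/(222 + 41q)

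- Low: 1 + 1.38/250.7 = 1.006
- High: 1 + 6.46/234.3 = 1.028

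In events, this is 82 × h × (1 − q) × e = 0.3 to 2.6 extra recorded hospitalizations across both acupuncture arms together.

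**The case against.** **A reader might infer that the under-count is worse in UMC.** Only SA and EA participants see a study acupuncturist, and the alert duty names hospitalization. But Protocol 7.3 and SAP 19.2 describe hospitalizations as identified by EHR query, which applies to all arms alike. Nothing says that alerts are added to the count behind the analytic reports or the SAP 19.5 tables. If they are not, they create no arm difference. IFH acupuncturists do chart in the IFH EHR (Protocol 5.1), so their notes could in principle reach the query, but the documents do not say that the query reads them. The differential is therefore a possibility, not a finding. If present, it would add recorded events in the acupuncture arms and so prompt review. It would not hide a harm, although the general under-count could weaken a true signal.

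**A reader might extend the point to Sutter Health,** since Protocol 9.6 says it provides most of its participants' care. SAP 18 says that all utilization can be captured there, so the documents do not support counting it.

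**The monitoring plan may already cover this.** SAP 19 and 19.4 refer to a data safety monitoring plan for detail, and it could name another IFH source. This stands as a caveat. Still, Protocol 7.3 and SAP 19.2 themselves specify how hospitalizations are found, and they name only the query.

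**Incomplete is not absent, and patient report is listed.** Some IFH hospitalizations will be in the EHR. The measures table in Protocol 6.2.2 lists patient report as a source for both adverse events and utilization. However, the adverse event questions described concern harm from acupuncture, and no safety section uses the utilization report.

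**Conclusion.** The under-count at IFH holds on the protocol's own statements. Followed as written, the plan looks for one class of SAE in a record that it elsewhere calls incomplete, for 15.6% of the sample. The size is not known: the 4 to 17 missed events rest on assumed hospitalization and capture rates, and the monitoring plan may reduce them. An arm difference remains conditional. Under the stated assumptions it could be visible within IFH (ratio 1.05 to 1.53) but is small trial-wide (about 1.01 to 1.03). The main consequence is serious events at IFH that go unreviewed and IFH counts that cannot be taken at face value, not a materially biased overall comparison. The efficacy analysis is unaffected. A cheap correction is worthwhile.

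**What to change.** **Protocol 7.3 and SAP 19.2.** Add one arm-neutral item to the existing 3-, 6- and 12-month surveys in all three arms, at least at IFH: whether the participant has stayed overnight in a hospital since the last survey, when and why. Send positive answers not already in the EHR to the site clinician's existing review. If the monitoring plan already provides an IFH source, cite it here.

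**SAP 19.5.**

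- Record the source of each hospitalization.
- Base the by-arm comparison, and the chart-review trigger in Protocol 7.3, on arm-neutral sources (EHR query plus survey).
- List separately the events known only from acupuncturists or spontaneous calls. At IFH, treat an event seen only in the acupuncture visit template as acupuncturist-only.
- State that IFH EHR-only counts are incomplete, and show the comparison with and without IFH.

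**Cost.** A protocol and IRB amendment, one survey item and a few SAP lines. Self-reported stays bring recall error, survey non-response may differ by arm, and diagnoses from outside hospitals may be unavailable to the clinician. On the assumed 10-20% rate, reconciliation covers about 12 to 25 people if limited to IFH (123 × 0.10 to 0.20), against 79 to 158 at all sites (789 × 0.10 to 0.20). The item does not ask about treatment, so it need not unmask interviewers. If follow-up is too far advanced for a new item, the SAP 19.5 changes can still be made with existing data.

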Objective 1 outcome data will be collected by questionnaire at 3-, 6-, and 12-months post-randomization. In addition, short monthly surveys will capture data on physical function and a composite score of pain intensity and pain interference.

Our primary outcome will be back-related dysfunction measured by the Roland Morris Disability Questionnaire and our primary timepoint will be 6 months. Key secondary outcomes include the PEG scale (a composite three-item scale assessing pain and pain interference). Other secondary outcomes will include the 6-item PROMIS physical function scale and patient global impression of change. Tertiary outcomes will include the two PROMIS 29 measures (fatigue, social function), the PHQ-4 screener for anxiety and depression and monthly measures of physical function and the PEG scale. We will collect data (EuroQol patient reported outcome scale and health care utilization from the electronic health record) for conducting a cost-effectiveness analysis (Objective 2). We will collect qualitative data from interviews and focus groups that are pertinent to our third objective.

Interventions and Duration

SA will consist of 3 months (90 days) of acupuncture needling, with a proposed minimum of 8

treatments and a maximum of 15. EA will include the standard acupuncture plus an additional 3-month maintenance period, with a proposed minimum of 4 additional acupuncture needling treatments and a maximum of six. UMC will consist of the care that individuals receive according to their insurance benefits plus anything else they pay for out of pocket. We will ask those assigned to UMC to avoid acupuncture for the year they are enrolled in the study. Both active treatment arms (SA, EA) will also have access to UMC as described above. Participants will be enrolled in the study for 12 months.

Sample Size and Population

We will include patients at least 65 years of age with uncomplicated cLBP with or without radiculopathy. We plan to enroll a total of 789 participants (263 per study arm), with the total number enrolled not to exceed 820 participants. Participants will be recruited from four health plans, with varying numbers of participants from each site. Randomization will be stratified by health care system, age category and gender. We expect the racial and ethnic mix will roughly parallel that of the older Medicare population.

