5. STUDY INTERVENTIONS

5.1 Interventions, Administration, and Duration

Acupuncture will be individually administered to patients by a licensed acupuncture practitioner in outpatient HCSs clinics or community acupuncturists' offices.

5.1.1. Standard acupuncture (SA):

Our SA intervention is based on classical Chinese acupuncture therapy and was developed with a team of experts using a modified Delphi process. It involves up to 15 acupuncture treatments over 3 months with the total number being determined by the patient and acupuncturist together. (Fifteen treatments is consistent with the greatest number of allowed treatments in some of the largest acupuncture trials to date.²⁸⁻³⁰) We encourage, however, a minimum of 6-8 treatments in the first 8 weeks,^{23,42} with at least 1-2 treatments in the last 4 weeks.^{24,25} The Acupuncture Advisory Panel recommended that we consider 8 treatments as the minimum for determining if the patient is not a responder to acupuncture. Treatment visits will typically last 45-60 minutes. All treatments will include only acupuncture needling, even though other adjunctive modalities (e.g., moxibustion or other forms of heat, cupping, gua sha, tui na) are typically part of practice.⁴³ Treatments will be provided at medical facilities or in private acupuncturists' offices.

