***Primary Outcome Measure (Roland Morris Disability Questionnaire)**

Blue measures are recommended by the NIH Task Force (RTF)

**CDE=HEAL Common Data Elements (required for all HEAL trials)

PROMIS-29 profile V 2.0, note we will add 2 additional questions to the Physical Function and Sleep Disturbance Measures to ensure measures in these domains reflect core HEAL measures. We will not be asking the Pain Intensity, Pain Interference, Depression or Anxiety Scales

[±] At 6-month timepoint only (Sleep duration is asked at all timepoints.)

#At 3- and 6-month timepoints only

^At 12-month timepoint only

Our approach to measurement includes adoption of many recommendations by the NIH Research Task Force for Low Back Pain (RTF),⁶⁰ the IMMPACT domains for clinical trials of chronic pain⁶¹ and the NIH PRISM HEAL Common Data Elements (CDE). In addition, we plan to harmonize as much as possible with the Optimum trial, which is also a study focused on cLBP. In considering measures to include in our assessment battery, we attempted to adopt as many of the HEAL CDE as we reasonably could while ensuring that constructs pertinent for our study target population were included and that redundancy and potential cognitive load was minimized to reduce burden on our older adult population.

Baseline Interview

When possible, we will obtain sociodemographic characteristics from the EHR including: birthdate (to calculate age), sex, race, and ethnicity but will verify this information at the baseline assessment as well as augment it with the “sex at birth” and “gender identity” questions from the HEAL Common Data Elements (CDE). Other sociodemographic variables will be obtained directly from the participant including: employment status, education, marital status, income, tobacco use, alcohol use, duration of pain condition. Further questions characterizing the

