Stakeholder participants will be invited for a 30-45 minute interview. Phone interviews will be recorded via Teams. The recording will begin after the interviewer briefly reviews the information sheet with the stakeholder participant to respond to any questions, and after the participant gives verbal consent to participate in the interview and be recorded (if the individual consents to the interview but not to be recorded, the interviewer will take notes to capture as much of the interviewee's responses as possible). The KPWHRI or KPNW staff performing the interview will take notes and will make a note in the REDCap database indicating whether the participant gave verbal consent to both participate and record the interview. If the interview is performed at KPNW, the recording will be sent to KPWA via secure file transfer for transcription.

The recording will be sent to a professional transcriptionist (Jackson Street Associates), with whom we have a Business Associate Agreement established, via secure file transfer to be transcribed. Interview transcripts will be returned to the study team via secure file transfer and stored in a secure project folder on the KP Washington network. Only BackInAction study staff will have access to the transcripts and will remove any identifiable information from the final transcripts. The audio files will be destroyed 5 years after the conclusion of the project.

Study staff will send an incentive of \$50 with a gift card to the stakeholder participant, if they are eligible to receive incentives, after completion of the interview.

Randomization

Patients will be randomized just after the baseline assessment has been completed. It is our intent that the baseline assessment is completed within a week of the eligibility screen (otherwise, back pain eligibility questions will need to be reassessed). Participants will receive \$15 for completion of the baseline assessment. Participants are asked to make their first visit to acupuncture within 10 days of being randomized.

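### Four accounts of when acupuncture participants are asked about non-serious adverse events disagree, and the most detailed one asks EA but not SA about month 4

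*Protocol*

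**What the plan says.** Four places set out when participants are asked about non-serious adverse events (AEs).

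- **Protocol 6.1 (Schedule of Evaluations):** the AE row is ticked under acupuncture visits and under the single column for 3, 6 and 12 months. No arm is named.
- **Protocol 6.2.2 (study measures table):** the AE row carries the footnote "At 3- and 6-month timepoints only". Again no arm is named.
- **Protocol 7.2 and 7.3:** a mailed form is "sent to all acupuncture-randomized participants at 3 months after randomization and enhanced acupuncture participants again at 6 months after randomization". It asks about problems that disturbed functioning for some days and that the participant attributes to study acupuncture.
- **SAP 19.1:** participants are asked at the 3-, 6- and 12-month assessments whether their acupuncture caused significant discomfort or pain, and for how long. SA and EA are not distinguished.

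Protocol 7.3 and SAP 19.1 add two further channels: acupuncturists' treatment reports, and phone calls from participants at any time. Deaths and hospitalizations are sought by monthly health-record queries.

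The AE period is also stated in two ways. Protocol 7.3 defines a non-serious AE as one that "occurs or worsens during the acupuncture intervention period and is plausibly related to acupuncture". It then says "we will not report AEs that first manifest more than 30 days after" the final treatment. SAP 19.1 repeats both statements. SAP 19.5 summarises safety outcomes by type and by intervention, including timing relative to randomization.

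**The concern.** Staff cannot carry out four schedules and two questions at once, and the choice between them decides which events are seen. Protocol 7.2 and 7.3 are the most detailed and agree with each other, so they are the likeliest to be followed. On that version SA gets one form and EA two.

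Two consequences follow. First, the last form can arrive before the 30 days after the final treatment have run out. Second, for part of month 4 the same late reaction to the standard course would be asked about in EA and not in SA. The by-arm AE table is where a reader will look for the harm of adding maintenance, and part of any difference there could come from asking more often.

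**Working it through.** The documents give no figure to reproduce, so this is a calendar check.

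**Inputs**
- SA length is 90 days: "SA will consist of 3 months (90 days) of acupuncture needling" (Protocol précis, Interventions and Duration).
- EA length is 3 + 3 months (Protocol 5.1.2), taken as 180 days.
- In the standard phase the protocol encourages 6-8 treatments in the first 8 weeks, "with at least 1-2 treatments in the last 4 weeks" (Protocol 5.1.1).
- Start of treatment: "Participants are asked to make their first visit to acupuncture within 10 days of being randomized" (Protocol 6.2.2, Randomization).
- Reporting limit: 30 days after the final treatment (Protocol 7.3, SAP 19.1).
- Form days: 3 × 365.25/12 = 91.3; 6 × 365.25/12 = 182.6; 12 months = 365.25.

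**Assumptions.** The form is answered when sent. The 6-month form reaches back to the 3-month one; the question as quoted sets no recall period. The treatment clock starts either at randomization (day 0) or at a first visit on day 10. Protocol 9.6 places maintenance between 3 and 6 months after randomization, which favours day 0.

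**Unasked tail under Protocol 7.2/7.3** = last treatment day + 30 − day of last form.

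| Arm | Clock start | Latest treatment | 30 days end | Last form | Tail |
|---|---|---|---|---|---|
| SA | day 0 | 90 | 120 | 91.3 | 28.7 |
| EA | day 0 | 180 | 210 | 182.6 | 27.4 |
| SA | day 10 | 100 | 130 | 91.3 | 38.7 |
| EA | day 10 | 190 | 220 | 182.6 | 37.4 |

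These are maxima.

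**Who is affected.** The tail is zero if the last treatment falls by day 91.3 − 30 = 61.3 in SA, or day 182.6 − 30 = 152.6 in EA. The last 4 weeks of a 90-day course are about days 62 to 90. An SA participant treated as encouraged therefore has a tail of 62 + 30 − 91.3 = 0.7 to 90 + 30 − 91.3 = 28.7 days.

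**Difference between the arms.** From day 91 to about day 120 (130 with a day-10 start), EA participants have maintenance-visit reports and the 6-month form. SA participants have neither.

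**The other schedules**
- Both arms at 3, 6 and 12 months (SAP 19.1; Protocol 6.1 read literally): the SA period ends by day 130, before day 182.6, and the EA period ends by day 220, before day 365. The gap is zero in both arms. EA participants would be recalling a period that ended 365 − 220 = 145 to 365 − 210 = 155 days before.
- Both arms at 3 and 6 months (measures-table footnote): the SA gap is zero, and the EA gap stays at about 27 to 37 days.

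**The case against.** The strongest reply is that SAP 19.1 and Protocol 6.1 already ask at 3, 6 and 12 months with no SA/EA restriction. On that schedule both the gap and the inequality vanish. That is correct, and it is why the main point is the contradiction and not a settled flaw in Protocol 7.3. It does not remove the problem. The footnote excludes 12 months, 7.2 and 7.3 exclude SA at 6 months, and the SAP question differs from the form. Protocol 7.4 and SAP 19.3 both speak of reviewing AEs from the 3- and 6-month questionnaires, without mentioning a 12-month one. The footnote may be shorthand for 7.3, but Protocol 6.1 and SAP 19.1 cannot be read that way. SAP 19 and 19.4 refer to a data safety monitoring plan that is not among the documents and might settle the matter.

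A second reply is that the 30-day sentence only says what will not be reported, while the definition refers to the intervention period. If the definition governs, one form at 3 months for SA and a second at 6 months for EA fits each arm's exposure closely. This is a fair reading. It shows that the two statements lead to different forms schedules and so need reconciling.

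A third reply is that the other channels remain open. Phone reports do, in both arms. Monthly record review still finds deaths and hospitalizations. For non-serious events after the last visit, however, acupuncturist reports stop and only an unprompted call is left.

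The protocol also describes acupuncture's effects as short-lived and says that nearly all AEs in its earlier studies resolved within 1-2 weeks. This limits the likely number of late events. It does not help with reactions to a treatment given just before the form, because the form asks about problems lasting some days.

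**Conclusion.** The concern stands as a set of passages that must be reconciled, with a real ascertainment gap if Protocol 7.2/7.3 is the version followed. The unasked tail is then at most about 29 days in SA and 27 in EA, or about 39 and 37 if the clock starts at a day-10 visit. Days 91 to about 120 are asked about in EA but not in SA. The AE period is stated inconsistently in both documents. No late-onset AE rate is given, so the number of missed events cannot be derived.

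A reader might infer more than the documents support:

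- **That all 263 SA and 263 EA participants are affected.** Those whose last treatment falls by about day 61 (SA) or day 153 (EA) are fully covered, and session numbers are flexible.
- **That SA is followed for a much shorter time after treatment.** The tails differ by only about one day. The inequality lies in the number of forms and in month 4, and EA's second form partly matches its longer exposure.
- **That EA will show more AEs through ascertainment alone.** SAP 19.5 plans a descriptive summary by arm and specifies no SA-versus-EA contrast for AEs. Partly confounded is as far as the text goes.
- **That serious events go unseen.** Monthly record review covers deaths and hospitalizations.

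**What to change.** 1. Bring Protocol 6.1, the 6.2.2 footnote, 7.2, 7.3 and SAP 19.1 to one schedule and one question, and align Protocol 7.4 and SAP 19.3 with them. Ask SA and EA alike at 3 and 6 months, with a later query that covers the end of EA's 30 days. The 12-month query in SAP 19.1 would do; a month-7 form to EA is optional and would shorten recall.
2. State the AE period once, so that the definition and the 30-day rule agree, in both documents.
3. In SAP 19.5, present non-serious AEs in SA and EA by source (form or query, phone, acupuncturist report) and over a common period. This remains possible if data collection is too far advanced to change the forms.
4. Say whether the question is mailed or asked in the assessment. Follow-up interviewers are to be masked (Protocol 6.2.3), and a question about acupuncture reactions could reveal the arm. Mailing it avoids this.

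The cost is about 263 extra forms or query items for SA at 6 months, plus review of positive answers. The optional month-7 form would add up to 263 for EA. No new instrument is needed.
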